6.4. Participant Recruitment and Screening

The Novoglan-01 Recruitment Plan is attached to this study Protocol and can be summarised as follows.

Target participants for the Novoiglan-01 study are males 18 years and over suffering from phimosis or tight foreskins. The accrual rate aims at 2 to 3 participants per months over the 12 to 18 months course of the study. The participant recruitment for the Novoglan-01 study will rely on the following means of advertising:

- Information Letter to general practitioners in [name] contact database located in greater Sydney. The draft wording of this document is presented in the Novoglan-01 Recruitment Plan.
- Information Letter to urologists in [name] contact database located in greater Sydney. The draft wording of this document is presented in the Novoglan-01 Recruitment Plan.
- Information Notice to the Sydney branch of the Royal Australian College of General Practitioners for advertisement on their website or newsletter. The draft wording of this document is presented in the Novoglan-01 Recruitment Plan.
- Poster advertisement to be placed in specific locations at Macquarie University. The proposed locations and the draft wording of this document is presented in the Novoglan-01 Recruitment Plan.
- Online advertising on the Novoglan website and dedicated Novoglan-01 web page. Details of this advertisement and draft wording of these documents is presented in the Novoglan-01 Recruitment Plan.

The Novoglan-01 Recruitment Plan also describes the logistics of referral processing to [name] secretariat and the participant compensation scheme to cover transport or parking costs.

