recommend the use of steroid creams or circumcision. The professional guidelines from the BAUS refer physicians to the guidelines published by the European Association of Urology (EAU) [EAU Guidelines, 2016] which address phimosis in the section dedicated to paediatric urology. The treatment recommendations include the use of steroid creams and if unsuccessful, the circumcision of the penis.

The main problem with using steroid creams to treat phimosis is the narrow range of stretching motion that will provide suitable stimulation for the foreskin to grow without exacerbating the inflammation or tearing of the foreskin. Recently, a new conservative treatment option, the Novoglan product, has shown promising results, with a very high success rate and satisfaction reported by users. The Novoglan product is designed to be used by participants 18 years and over. Its main component is a small balloon that can be inserted underneath the opening of the foreskin and progressively inflated while avoiding the complications frequently observed with the use of steroid creams. The Novoglan balloon is guided under the foreskin between the glans and the inner side of the foreskin (prepuce) using a purpose moulded rod. Once the balloon is in place the rod is removed and the stop cock and plunger is attached to the Novoglan device. The balloon is inflated by pressing the plunger. The procedure is painless and pressure is under the control of the user to ensure no discomfort. Foreskin cells are placed under tension and tight junctions are loosen under stretching leading to tissue adaptation and cell mitosis. This process increases the column of foreskin cells and increases the foreskin circumference. Treatment is continued for a period of 4 to 8 weeks until full normal retraction is achieved.

The Novoglan product is a medical device commercialised in Australia since 2006 and listed with the Australian Therapeutics Goods Administration (ARTG 168962). The Novoglan product has been used successfully in the Urology Clinic in the past year at Macquarie University Hospital but only with a few adult male participants. The observation of these few adult participant treatments indicated that the Novoglan product is simple and safe to use, effective at treating adult phimosis and comparatively inexpensive. It appears that the Novoglan product produces relief from the symptoms of phimosis in 3 to 4 weeks.

References, in order of citation, are as follows.

The prepuce.

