5. STUDY PARTICIPANTS

5.1. Inclusion Criteria

The Novoglan-01 study inclusion criteria are as follows.

1. Male 18 or older referred to the urology clinic
2. Symptoms of adult phimosis with inability to fully retract the foreskin
3. Reporting of pain or discomfort

4. Potential participant may have Balanitis Xerotica Obliterans or undergone prior frenuloplasty
5. Willingness to provide informed consent and willingness to participate and comply with the study requirements.

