5.2. Exclusion Criteria

The Novoglan-01 study exclusion criteria are as follows.

1. Any known allergy to latex or silicones
2. Any bleeding, ulcer or active infection of the penis
3. Any prior prepuce surgery, except for frenuloplasty
4. Any hypospadias
5. Any severe scarring of the glans or foreskin
6. Any history of penile cancer
7. Participants with a history of a psychological illness or other conditions which may interfere with their ability to understand the study requirements

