6.2. Investigation Plan

Methodology

This section clearly describes how the study procedures/interventions will be conducted in order to ensure the results are reproducible. It includes a table listing all the potential study visits and the procedures that will be conducted at each visit.

Interventions	Enrolment Visit	Visit 1	Visit 2 (phone)	Visit 3 (phone)	Final Study Visit
Timing	Week 0	Week 1	Week 2	Week 5	Week 7 to 9
Baseline demographics	✓				
Medical history	✓				
Concomitant medications	✓		✓	✓	✓
Inclusion / Exclusion criteria	✓				
Participant Consent	✓				
Phimosis measurement		✓			✓
Quality of life questionnaire		✓			✓
Novoglan supply and training		✓			
Treatment progress, adverse event or complication			✓	✓	✓
Treatment tolerability questionnaire					✓

The participant journey during the Novoglan-01 study can be described as follows.

Enrolment visit

Potential participants identified during the Novoglan-01 recruitment process will be seen by the Principal Investigator, [name], during the Enrolment Visit. At that time, the following information will be collected from the participant:

- Demographics including date of birth, race and ethnicity
- Medical and medication history, with particularly focus on phimosis
- Penile examination to confirm phimosis and medical examination including height and weight measurements
- Review of eligibility for the Novoglan-01 study against inclusion and exclusion criteria

If the participant meets the eligibility criteria, [name] will propose participation into the Novoglan-01 study, explain the study, explain the informed consent and review with the participant the informed consent form, pointing out the option of withdrawal at any time and the minimum delay of 1 week between Enrolment Visit and Study Visit 1 to provide sufficient time for careful consent consideration.

At that time, participants wanting to participate in the Novoglan-01 study will:

- Sign the Novoglan-01 Informed Consent Form (see details in Section 9)
- Be asked to make an appointment for Study Visit 1 with the Clinical Trial Nurse
- Be assigned a Novoglan-01 Study unique participant identifier

If the participant agrees to participate to the Novoglan-01 Study, all the above information will be recorded by [name] in the Participant Case Report Form (see details further in Section 9).

Study Visit 1

At Study Visit 1 the participant will meet with the Clinical Trial Nurse who will:

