6.5. Participant Enrolment

Potential participants will be enrolled into the study after the informed consent process has been completed and the participant has been assessed to meet all the inclusion criteria and none of the exclusion criteria and provided full demographics, relevant medical history of phimosis and concomitant medication information. Study participants will receive a study enrolment number and this will be documented in the participant's medical (or personal) record and on all study documents.

Study participants will also be offered to have clinical trial cost travel or parking expenses reimbursed in line with guidelines stated in the *ICH Harmonised Guidelines for Good Clinical Practice E6(R2)* dated November 2016.

Once formally enrolled in the Novoglan-01 study and following signature of the **Participants Information Consent Form** (attached to this study protocol), a date for the first Novoglan-01 Visit 1 or arrangements on how to schedule Visit 1 will be provided to the enrolled participants.

The scheduling of Study Visit 1 will ensure that this date is at least 1 week after the Enrollment Visit, thus providing sufficient time for participants to consider their informed consent and if need be to withdraw from the study prior to receiving any treatment intervention.

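### Neither eligibility list bars previous or current Novoglan users, so some Visit 1 values may not be true pre-treatment values and tolerability may come partly from self-selected men

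*Protocol*

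**What the plan says.** **Eligibility.** The disease criterion in Protocol 5.1 is "Symptoms of adult phimosis with inability to fully retract the foreskin", together with pain or discomfort and referral to the urology clinic. It does not ask that the man be new to the device. Of the seven exclusions in 5.2, the only one about earlier treatment of the foreskin is "Any prior prepuce surgery, except for frenuloplasty". Section 6.5 makes these lists decisive: a man is enrolled once "the participant has been assessed to meet all the inclusion criteria and none of the exclusion criteria" and his consent and history are complete.

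**Availability of the device.** The background section states "The Novoglan product is a medical device commercialised in Australia since 2006". On the recruiting clinic it says "The Novoglan product has been used successfully in the Urology Clinic in the past year at Macquarie University Hospital but only with a few adult" men.

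**Recruitment.** Section 6.4 lists five channels: letters to general practitioners, letters to urologists, a notice through the general practitioners' college, campus posters, and "Online advertising on the Novoglan website and dedicated Novoglan-01 web page".

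**What is measured and when.** The phimosis grade and the quality-of-life questionnaire are taken at Visit 1, when the product is supplied, and again at the Final Study Visit (6.2). Tolerability is asked once, at the end. The Enrolment Visit collects "Medical and medication history, with particularly focus on phimosis", but previous use of the device is not named there.

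**The concern.** The primary endpoint (4.4) is improvement in foreskin retraction, and quality of life is compared before and after treatment. Both need a Visit 1 value that comes before treatment, and section 6.2 describes the Visit 1 quality-of-life assessment in that way. For a man already using the device on his own account, that description is untrue.

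The second issue is selection. A man who found the device uncomfortable and gave up is less likely to volunteer for it again than one who got on with it. If earlier users enter, the tolerability and satisfaction results may describe men who already accept the device. Section 6.3 says that the product's safety has never been scientifically analysed, and section 7.1 hopes to support its use as a first-line conservative option. A man who has already used the device says little about either for a new user. The study is single-arm and open-label (6.7), so no comparison group shares and cancels these effects.

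**Working it through.** The Protocol gives no count of earlier users and no figure on this point, so there is nothing to reproduce. The check is mainly a reading of sections against each other.

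**Step 1: can an earlier or current user be enrolled?** Take a man part-way through a course he bought himself. The background section describes a course of 4 to 8 weeks.
- 5.1: adult and referred to the clinic (possible); still unable to retract fully (yes, if the course is unfinished or has failed); discomfort (possible); consents (yes).
- 5.2: none of the seven exclusions is triggered by device use.
- 6.5: with every inclusion met and no exclusion met, he can be enrolled.

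**Step 2: would the history taken at enrolment stop him?** It might bring his use to light, but no criterion or action follows from it. Section 12.1 classes the product as a medical device and not a therapeutic product, so a medication list need not show it.

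**Step 3: who among earlier users is left?** Men in whom the device fully worked no longer meet the retraction criterion. The remaining pool is unfinished courses, partial responders, failures and relapses.

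**Step 4: direction, endpoint by endpoint.**

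| Type of man | Phimosis change from Visit 1 | Tolerability and satisfaction |
|---|---|---|
| Current user or partial responder | Starts from a better grade, so less room to improve; may also be a known responder. Direction open | Plausibly favourable |
| Earlier failure | Plausibly lowers efficacy | Plausibly favourable if he tolerated the device and chose to return |

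**Step 5: size.** No effect size follows from the document. To show only how a mixture behaves, let k of 24 men be earlier users, with success proportions p in naive men and q in earlier users:

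overall = ((24 − k)·p + k·q) / 24

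All values of k, p and q below are assumptions.

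| k | p = 60%, q = 90% | p = 60%, q = 30% |
|---|---|---|
| 0 | 60% | 60% |
| 2 | (22·0.6 + 2·0.9)/24 = 62.5% | (22·0.6 + 2·0.3)/24 = 57.5% |
| 4 | (20·0.6 + 4·0.9)/24 = 65% | (20·0.6 + 4·0.3)/24 = 55% |
| 6 | (18·0.6 + 6·0.9)/24 = 67.5% | (18·0.6 + 6·0.3)/24 = 52.5% |

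The shift runs from 2.5 to 7.5 points, upward or downward according to the assumed q. It applies to a proportion, whereas the primary outcome in 8.2 is an ordinal scale, so it does not estimate bias in the primary analysis.

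**The case against.** The case against has real force.

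- **Few men.** The clinic had treated only a few men, and the Protocol calls that use successful. Successes cannot re-enter, so the clinic's own patients add very little. This stands, and the point does not rest on them.
- **The website also reaches first-time buyers.** It is one of five channels, and entry requires referral and examination by the investigator. The document does not show that any earlier user would come through it. This stands as to number, but it does not close the gap in the criteria.
- **Visit 1 absorbs earlier benefit.** Improvement gained beforehand is already in the baseline grade. This is largely right for the phimosis grade. It does not make a current user's baseline a pre-treatment one, and it does nothing for tolerability, which has no baseline.
- **The history taken would reveal it.** Perhaps, but nothing is done with the answer. Whether recruitment source is recorded cannot be judged, because the case report forms and Recruitment Plan are not shown. No criticism is made of that.
- **The cohort is meant to be inclusive.** It admits men with Balanitis Xerotica Obliterans or prior frenuloplasty and does not exclude earlier steroid cream. That is a fair design choice, but earlier use of the test device itself bears directly on a before-and-after comparison.

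A reader might infer that experienced users could drive the efficacy result, or that each one moves it by 1/24 = 4.2 percentage points (8.3 for two, 16.7 for four). The document does not support this. Those figures hold for any participant with any characteristic, assume a complete switch from failure to success, and concern a proportion when the primary outcome is ordinal. The number of such men and the direction for efficacy are both unknown.

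**Conclusion.** The gap is real but modest. The criteria allow a current or earlier Novoglan user who still has symptomatic phimosis to be enrolled, and for a current user the Visit 1 phimosis grade and quality-of-life score are not true pre-treatment values. The bias in the primary endpoint could go either way. Tolerability and satisfaction would plausibly look better, on the assumption that men who return to a device are more often those who tolerated it. The number affected is not given and is probably small, and no effect size can be derived. The point is worth acting on because the remedy is cheap, the trial has no control arm, and prior use may be hard to establish later if it is not recorded at enrolment.

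**What to change.** Add one exclusion to Protocol 5.2: previous or current use of the Novoglan product. Ask about it within the medical history already taken at the Enrolment Visit, so no extra visit or procedure is needed.

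If any earlier users have already been enrolled, record this for each of them, and report the primary and secondary outcomes for device-naive participants only alongside the results for all participants.

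The cost is one eligibility line and one question. A few otherwise eligible respondents would be lost, probably from the website channel, and accrual may be slightly slower.

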6.5. Participant Enrolment

Potential participants will be enrolled into the study after the informed consent process has been completed and the participant has been assessed to meet all the inclusion criteria and none of the exclusion criteria and provided full demographics, relevant medical history of phimosis and concomitant medication information. Study participants will receive a study enrolment number and this will be documented in the participant's medical (or personal) record and on all study documents.

Study participants will also be offered to have clinical trial cost travel or parking expenses reimbursed in line with guidelines stated in the *ICH Harmonised Guidelines for Good Clinical Practice E6(R2)* dated November 2016.

Once formally enrolled in the Novoglan-01 study and following signature of the **Participants Information Consent Form** (attached to this study protocol), a date for the first Novoglan-01 Visit 1 or arrangements on how to schedule Visit 1 will be provided to the enrolled participants.

The scheduling of Study Visit 1 will ensure that this date is at least 1 week after the Enrollment Visit, thus providing sufficient time for participants to consider their informed consent and if need be to withdraw from the study prior to receiving any treatment intervention.

6.6. Information and Consent

Novoglan-01 study investigators must ensure that participants are clearly and fully informed about the purpose, potential risks, and other critical issues regarding clinical studies in which they volunteer to participate. In situations where consent cannot be given to participants, their legally acceptable representatives are clearly and fully informed about the purpose, potential risks, and other critical issues regarding clinical studies in which the participant volunteers to participate. Participants will be provided with an appropriate sample informed consent form, which will include all elements required by ICH GCP and applicable regulatory requirements. The sample informed consent form adheres to the ethical principles that have their origin in the Declaration of Helsinki. Investigators must:

1) Provide a **copy of the consent form and written information about the study** in the language in which the participant is most proficient prior to clinical study participation. The language must be non-technical and easily understood. **A copy of the Novoglan-01 study Participant Information and Consent Form is attached to this Protocol.**

2) Allow **time necessary for participant or participant's legally acceptable representative to inquire about the details** of the study. During the Enrollment Visit and if the participant meets the eligibility criteria, [name] will propose participation into the Novoglan-01 study, explain the study, explain the informed consent and review with the participant the informed consent form, pointing out the option of withdrawal at any time and the minimum delay of 1 week between Enrolment Visit and Study Visit 1 to provide sufficient time for careful consent consideration.

3) Obtain an ***informed consent signed and personally dated by the participant***. This will be completed as mentioned above.

4) Obtain ***the IRB/IEC's written approval/favourable opinion*** of the written informed consent form and any other information to be provided to the participants, prior to the beginning of the study, and after any revisions are completed for new information. A copy of the Novoglan-01 study Participant Information and Consent Form will be submitted for review to the Macquarie University Health Research Ethics Committee review.

5) ***Revise the informed consent whenever important new information becomes available*** that is relevant to the participant's consent. The investigator, or a person designated by the investigator, should fully inform the participant, of all pertinent aspects of the study and of any new information relevant to the participant's willingness to continue participation. Any revision to the Novoglan-01 study Participant Information and Consent Form will be carried out if important new information becomes available that is relevant to the participant's consent.

6.7. Randomisation Procedure

The Novoglan-01 study does not require randomisation. It is a single arm, observational, open label, prospective clinical trial on a cohort of 24 participants all undergoing the same treatment with a product listed as a Class 1 device by the Australian Therapeutics Goods Administration for the treatment of adult phimosis.

6.8. End of Study Treatment

At the end of a Novoglan-01 study and during the Final Study Visit, each participant will be:

- Measured for phimosis using the same measuring scale as used during Visit 1
- Surveyed for any adverse effect experienced during the study and not as yet reported
- Surveyed for quality of life using the same questionnaire as used during Visit 1
- Surveyed for tolerability of treatment using a purpose-designed questionnaire

Finally, at the end of each participant Final Study visit, all clinical trial documents related to the participant will be collected and stored in the ***Clinical Trial Master File*** for subsequent analysis and storage as per guidelines from the Australian Clinical Trial Handbook Version 2.0 dated March 2018.

6.9. Participant Withdrawal

The voluntary participant withdrawal during the Novoglan-01 Study Protocol follows the guidelines from the ***National Statement on Ethical Conduct in Human Research*** (2007, updated 2018).

Voluntary withdrawal

Participants enrolled in the Novoglan-01 clinical trial are entitled to withdraw at any stage. Before consenting to be involved in the Novoglan-01 study, participants will be informed about any consequence of such withdrawal. The withdrawal of any participant will be registered by the signature by both the Principal Investigator and the withdrawing Participant of the ***Novoglan-01 – Form for Withdrawal of Participation*** attached to this study protocol. Participants withdrawing prior to visit 1 where investigative product and training is provided will be replaced.

7. OUTCOMES

7.1. Definition of Outcomes

The expected outcomes from the Novoglan-01 study are as follows.

- Confirmation of the ability of the Novoglan product to effectively relieve phimosis as measured by foreskin retraction before and after treatment against the Phimosis Measurement Scale used at Study Visit 1 and Final Study Visit.
- Confirmation of the safety of the Novoglan treatment as evidenced by the lack of any severe adverse effect or any complication during treatment.
- Confirmation of the satisfaction of participants with the Novoglan treatment as measured by improved quality of life measured by questionnaire filled in by the participants before and after treatment.
- Confirmation of the tolerability of the Novoglan treatment as measured by the treatment tolerability questionnaire filled in by the participants during the Final Study Visit.
- Confirmation of the Novoglan treatment as a valid conservative first line treatment alternative to steroid creams in adult males presenting with phimosis.

Additionally, the publication of the Novoglan-01 study results at urology conferences and in a peer review journal is likely to encourage a review of clinical recommendations in the treatment of adult phimosis. Phimosis treatment guidelines published by the British Association of Urological Surgeons (BAUS) discourage the manual stretching of the foreskin and recommend the use of steroid creams or circumcision. The professional guidelines from the BAUS also refer physicians to the guidelines published by the European Association of Urology (EAU) which address phimosis in the section dedicated to paediatric urology.

Assuming a positive outcome from the Novoglan-01 study that demonstrates the safety, efficacy and tolerability of the Novoglan product in adult phimosis, the aim would be to:

- Convince the phimosis treatment guidelines published by the Urology Society of Australian and New Zealand (USANZ), EAU or BAUS to include a section dedicated to the treatment of adult phimosis.
- Convince the phimosis treatment guidelines published by the USANZ, EAU or BAUS to list the Novoglan product as a recommended conservative treatment for adult phimosis

Finally, the publication of the Novoglan-01 study results is likely to position MQ Health as the centre of reference for adult phimosis treatment in Australia. It is also likely to stimulate similar studies in Australia and overseas.

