4.2. Expected Participant Numbers

The Novoglan-01 study is expected to enroll 24 participants.

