4.4. Endpoints

Primary Endpoints

Primary endpoint – Efficacy of the device demonstrated by the improvement in foreskin retraction as measured using the Kikiros-inspired phimosis assessment scale.

Secondary Endpoints

First secondary endpoint – Safety of the device as evidenced by the reporting of any adverse effect or complication as observed and noted by the clinical trial team during the participant's treatment.

Second secondary endpoint – Participant satisfaction with the treatment as confirmed by treatment tolerability reported by the participant with a standardised treatment tolerability questionnaire and improvement in quality of life post-treatment as assessed by a standardised quality of life questionnaire before and after treatment.

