6.3. Study Procedure Risks

The following risk assessment for the Novoglan-01 study was prepared using Trial Risk Assessment for the NSLHD Investigator-led/Collaborative Group Clinical Trials published by the NSW Department of Health, Version 2.0 dated April 2016 (on file at Platigo Solutions).

Additionally, all measures designed to reduce risks are presented in the **Novoglan-01 clinical trial Safety Plan** submitted for review together with the Study Protocol.

- Participant Journey

The participant journey is described above in section 6.2.

- Additional risks with participants' physical integrity and safety

The Novoglan-01 study involves a medical device that is currently listed on the Australian Therapeutics Goods registry under the reference #168962 as a Class 1 (non-sterile) device indicated for the treatment of phimosis in adults. Furthermore, the Novoglan product will be used as per indications in the device TGA listing during the Novoglan-01 clinical trial.

Despite the Novoglan product having been commercialised without any reported adverse event, the Novoglan product safety has never been scientifically analysed and it is therefore reasonable to consider the study risk as Type B or somewhat higher than that of standard of medical care for adult phimosis, the standard of care being either the use of steroid creams or circumcision.

- Safety monitoring of the trial and DSMC

The establishment of a Data Safety and Monitoring Committee (DSMC) is not considered being necessary in view of the Type B risk category of the Novoglan-01 clinical trial and the fact that the Novoglan product will be used as on male adults as per usage instructions described in the listing of the device with the TGA.

- Risks to participants' rights

Risks to participants rights in taking part to the Novoglan-01 study have been assessed and mitigation strategies developed to minimise these risks. The risks evaluated fall into 2 categories and are presented in the following table.

Risks to participants' rights – The consent process		
Risk	Concerns	Risk minimisation strategy
Consent procedure	Does the consent process allow sufficient time for participants to consider their decision and discuss it with third parties	
 • Specific training on the consent/assent process will be provided to the clinical team. • First study visit following participant enrolment will be scheduled at least 1 week following the enrollment visit.

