8.1. Sample Size or Power Calculation

A power calculation was performed to assess which sample size (N) was appropriate for the Novoglan-01 clinical trial. Calculations show that 29 participants must be recruited to reach N = 24, considering a potential drop-out rate of 20%.

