8.2. Detailed Analysis Plan

The Novoglan-01 clinical trial involves the following measurement variables, which will be measured pre- and post-treatment:

Primary outcome variable (ordinal, scalar): Kikiros-inspired phimosis assessment scale (Kikiros, Beasley & Woodward 1993)

Secondary outcome variable (ordinal, scalar): A standardized treatment tolerability questionnaire

Secondary outcome variable (ordinal, scalar): A QoL scale questionnaire

The trial will also involve descriptive variables collected for each patient:

Physical parameters (e.g. age, weight, height – numerical variables)

Medical history (categorical, binary)

Record of Adverse Events (categorical, binary)

Evaluating Patient Descriptive Variables

The recommended analysis plan for the descriptive variables is to use a univariate analysis to contribute to the descriptive statistics of N. From there, tables showing frequency with medians, range, and standard deviations can be generated to describe the population.

Evaluating the Primary and Secondary Outcome Variables

An initial validation of each primary and secondary outcome variable will be applied using the Principal Component Analysis. If this analysis is successful, then each variable will be evaluated in an ordinal regression model (De Leeuw, Mair & Groenen 2017). If the outcome variables are to be evaluated at the same time, then a Multivariate Multinomial Logit Model will be applied (Bel & Paap 2014).

Further tests may be applied to evaluate any distributions and homogeneity within and between descriptive and outcome variables such as a Chi-Squared Test, Linear-by-linear Association Test, or Mann-Whitney U Test.

REFERENCES

- Bel, K. & Paap, R. 2014, A Multivariate Model for Multinomial Choices.
- R Development Core Team 2017, *R: A Language and Environment for Statistical Computing*, Vienna, Austria., R. Found. Stat. Comput., vol. 1.

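### Section 7.1 treats the absence of severe events or complications as confirmed safety, which about 24 men cannot show, and Section 8.2 leaves the safety endpoint of Section 4.4 out of its outcome variables

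*Protocol*

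**What the plan says.** Section 7.1 (Definition of Outcomes) gives as one of the study's expected outcomes "Confirmation of the safety of the Novoglan treatment as evidenced by the lack of any severe adverse effect or any complication during treatment". It states no acceptable event rate and no confidence limit. The same section then says that, if the study demonstrates safety, efficacy and tolerability, the aim is to persuade urology guideline bodies to list the product as a recommended treatment.

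Section 4.4 ranks safety directly after the primary endpoint: "First secondary endpoint – Safety of the device as evidenced by the reporting of any adverse effect or complication".

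Section 8.2 names two secondary outcome variables, tolerability and quality of life. Adverse events come under a different lead-in, "The trial will also involve descriptive variables collected for each patient", beside physical parameters and medical history. The entry begins "Record of Adverse Events (categorical, binary". The use given for this group is frequency tables that characterise the study population.

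On size, Section 4.2 says "The Novoglan-01 study is expected to enroll 24 participants", while Section 8.1 says "Calculations show that 29 participants must be recruited to reach N = 24, considering a potential drop-out rate of 20" per cent. On prior evidence, Section 6.3 says "the Novoglan product safety has never been scientifically analysed".

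**The concern.** Seeing no events in a small group is weak evidence that events are rare. Section 7.1 nevertheless equates it with confirmed safety, and it is the only place in the protocol that says what would count as evidence of safety. Because the product's safety has had no scientific analysis so far, this trial would supply the first. There is no comparator arm to put an observed count in context. A report that followed the text as written could tell guideline bodies that safety is confirmed when a rate above one in ten has not been excluded.

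The mismatch between Sections 4.4 and 8.2 adds to this. An endpoint ranked first among the secondaries does not appear among the outcome variables of the analysis section, so the protocol does not make clear that a safety analysis as such will be reported.

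**Working it through.** **The plan's own figure.** The protocol gives no figure for safety precision. Its only related number is the recruitment target in Section 8.1. Multiplying, 24 × 1.2 = 28.8, which rounds up to the stated 29. Dividing by the retained fraction, 24 / (1 − 0.20) = 30. The difference of one man is immaterial here. What matters is that the 24 in Section 8.1 is already net of drop-out.

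**Inputs.**
- Number treated: 24 (Section 4.2), or up to 29 if all recruits in Section 8.1 receive the device. Under Section 6.9, men who withdraw before Visit 1, when the device is supplied, are replaced, so a range of 24 to 29 treated is reasonable.
- Events observed: 0, the case that Section 7.1 describes.
- Confidence level: 95%. The protocol states none, so this is an assumption, and one-sided and two-sided limits are both shown.

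**Upper limit with zero events.** The chance of no event in n men at true rate p is (1 − p)^n. Setting this equal to α and solving gives the exact (Clopper-Pearson) upper limit, p = 1 − α^(1/n), with α = 0.05 one-sided and 0.025 two-sided.

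| Treated | One-sided 95% | Two-sided 95% |
|---|---|---|
| 24 | 1 − 0.05^(1/24) = 11.7% | 1 − 0.025^(1/24) = 14.2% |
| 29 | 1 − 0.05^(1/29) = 9.8% | 1 − 0.025^(1/29) = 11.9% |

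The rule of three agrees: 3/24 = 12.5%.

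**Chance that a real risk goes unseen in 24 men** (illustrative rates, not taken from the protocol):
- true rate 2%: 0.98^24 = 62%
- true rate 5%: 0.95^24 = 29%
- true rate 10%: 0.90^24 = 8%

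**Size needed.** To exclude a 5% rate with zero events at one-sided 95%, n must be at least ln(0.05)/ln(0.95) = 58.4, so 59 men. For a 2% rate the figure is 149.

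**Sections 4.4 and 8.2 side by side.** Section 4.4: safety is the first secondary endpoint. Section 8.2: the secondary outcome variables are tolerability and quality of life only, and adverse events are a descriptive variable. Both are current text.

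**The case against.** The best defence is that Section 7.1 lists hoped-for results and sets no test. The text that governs safety, in Sections 3.2 and 4.4, speaks only of observing and reporting events. That is correct. A reader might infer from Section 7.1 that a single minor complication would refute safety, but the protocol contains no such pass/fail rule, so failure probabilities for one should not be computed. The wording still equates absence with confirmation, and the section builds its guideline aim on a demonstration of safety.

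A second defence is that Section 8.2 only summarises a separate Statistical Plan, and that the Safety Plan and case report forms may record severity and device relation. This also stands. A reader might infer that a yes/no record cannot separate severe from mild events, but the documents do not show this: the label could cover several yes/no items, and those attachments are not at hand. Frequency tables are, moreover, close to what a descriptive safety analysis needs. What remains is the difference in status between Sections 4.4 and 8.2.

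Third, a reader might apply the 20% drop-out to the 24 and use a smaller denominator. Section 8.1 does not support that, because its 24 is already net of drop-out, and a man who stops after receiving the device still counts for safety.

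Finally, the protocol sets no acceptable event rate, so no particular threshold can be said to have been missed. The point is only that the data cannot justify the word confirmation.

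**Conclusion.** The point holds in a limited form. With zero events, the planned cohort leaves a true rate of up to 11.7% (one-sided) or 14.2% (two-sided) compatible with the data if 24 are treated, and 9.8% or 11.9% if 29 are. That does not amount to confirmed safety. The figures rest on an assumed 95% level and on one independent yes/no outcome per treated man; the 5% rate behind the 29% figure is an illustration. Separately, the protocol should say the same thing about the status of safety in Sections 4.4 and 8.2. The point does not extend to how adverse events are coded, and it does not treat Section 7.1 as a formal decision rule.

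**What to change.** In Section 7.1, replace the safety bullet with text such as:

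> Safety will be described by the number and proportion of all participants who received the device with any adverse event, any device-related adverse event and any serious adverse event, using the definitions in Section 12.1, each with an exact 95% confidence interval based on the number actually treated. If no event of a given kind is seen, this will be reported with its upper confidence limit and not as confirmation of safety.

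The upper limit should be calculated from the final number treated and not fixed in advance, since that number may differ from 24.

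In Section 8.2, name adverse events as the safety secondary endpoint of Section 4.4 under a separate descriptive safety analysis. They should not simply be added to the existing outcome list. Variables there are measured before and after treatment and go through Principal Component Analysis and ordinal regression; events during treatment have no baseline value, and sparse yes/no data suit neither method.

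The cost is wording in the protocol and, where needed, matching wording in the Statistical Plan. No extra participants are needed. The price is a less favourable safety statement.
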